8.3.5 Serious Adverse Events Requiring Discontinuation of Study Drug

To ensure the safety of study participants, study drug administration will be discontinued in any patient who experiences an SAE that is assessed by the Investigator as possibly related or probably related to study drug; the Investigator will assess if study drug administration will be discontinued in any patient who experiences an SAE that is assessed as not related to study drug.

The procedures for discontinuation of study drug and necessary follow-up and documentation are summarized in Section 8.3.6 and Section 11.5; also refer to Section 11.4 for instructions for completing the follow-up SAE form.

In addition, when a patient discontinues study drug secondary to the occurrence of a possibly related or probably related SAE, this is considered a "withdrawal due to an AE of interest", and the Investigator must provide a narrative describing the history and reason for withdrawal (see Section 11.1.1).

8.3.6 Instructions for Discontinuation of Study Drug Administration for Safety Concerns

See Section 11.5 for instructions upon a decision to permanently discontinue administration of study drug due to an AE, laboratory abnormality, or SAE. If permanent discontinuation of study drug is due to a reported SAE, a follow-up SAE report form should be completed (see Section 11.4).

8.4 Method of Assigning Patients to Treatment

8.4.1 Blinding and Randomization

8.4.1.1 Screening Procedures

All patients who are screened (including screen failures) will be assigned a patient number by the Interactive voice/web-Response System (IXRS). The unique patient identification number will consist of 6 digits (xxx-xxx), the first segment of the number represents the study site and the second segment of the number represents the patient at that study site. Any patient identification number that is assigned will not be reused even if the patient is not randomized.

8.4.1.2 Randomization

Randomization will take place using IXRS. Patients will be randomized after the Investigator has verified that they are eligible per criteria in Section 7. Patients will be randomized to receive either IMO-8400 at a dose of 0.6 or 1.8 mg/kg/week or placebo once a week for 24 weeks. Randomization will be performed centrally in a 1:1:1 ratio and will be stratified by baseline CDASIV2-Activity score (15 to 20 vs ≥ 21). A permuted block randomization schedule will be employed. Blocks will be pre-allocated to the two CDASIV2-Activity strata (15 to 20 vs. ≥ 21) to achieve a balanced distribution of treatment assignments within those groups.

8.4.1.3 Blinding

Every attempt should be made to preserve the integrity of study drug blinding. Except for cases of emergency unblinding as described in Section 8.4.2, the randomization code will remain unbroken for patients, parents/caregivers, and study personnel until the database has been locked.

Because SC administration of IMO-8400 has been associated with potentially unblinding ISRs, the mCDASIV2, MMT8, and timed function tests (10MWR, TUG, and 4 stair climb tests) will be performed by qualified and trained raters who will be blinded to treatment assignment and study drug injection sites and who will have no other role or responsibility in the study other than administration of these efficacy assessments. In addition, patients will be asked to wear clothing that covers all injection sites whenever they visit the study site.

8.4.2 Emergency Unblinding

In the event of a medical emergency, laboratory abnormalities or SAE requiring cessation of treatment, unblinding is not required to provide effective medical intervention and support.

In the exceptional circumstance that knowledge of the study drug assignment appears essential for providing appropriate medical management and in cases where an immediate need for unblinding exists for reasons of patient safety, the Investigator can unblind the patient's data at his/her discretion. When possible, the Investigator should consult the CRO Medical Monitor prior to unblinding to discuss the rationale for breaking the blind and the adverse consequences of the unblinding for the patient's continued participation in the study. The treatment assignment for that patient will be provided to the Investigator via the IXRS as described in the Study Reference Manual (SRM). No randomization lists or other unblinding information will be provided to the site.

After breaking the blind, the site staff should record details regarding the reasons for breaking the blind and any AEs leading to the breaking of the blind in the source documents and the appropriate electronic case report form (eCRF).

8.5 Treatment Compliance

Treatment compliance will be assessed via compliance with scheduled weekly injections and documented on appropriate pages of the eCRF.

9 PRIOR AND CONCOMITANT MEDICATIONS

Investigators may prescribe concomitant medications or treatments deemed necessary to provide adequate supportive care. Information regarding any prior and concomitant medications will be collected and documented in the eCRF and in the source documents by the clinic staff as described in the explanation of study procedures.

9.1 Permitted Concomitant Medications

The following therapies are permitted for use during the 24 weeks of study drug treatment as detailed in Table 4:

- Corticosteroids
- Non-steroidal immunomodulatory medications - no more than 1 of the following: IVIG, mycophenolate mofetil, cyclophosphamide, cyclosporine, leflunomide, tacrolimus, methotrexate, azathioprine
- Topical corticosteroids for use on the scalp only

Any other treatments (including prescription drugs, non-prescription drugs, and herbal remedies), except those listed in the prohibited concomitant medications section (Section 9.3) should be taken as prescribed, per Investigator judgment.

9.2 Stabilization and Washout Period for Permitted Concomitant Medications

For patients who are on corticosteroids or non-steroidal immunomodulatory medications, a stable regimen should be established as described in Table 4 prior to Screening and maintained during the 24 weeks of study drug treatment. Adjustments in dosage for increases in body weight are permitted but are not mandatory.

Table 4. Stable Regimens of Permitted Concomitant Medications

Category	Medication	Dose	Duration of Stable Regimen Prior to Screening
Corticosteroids	Oral prednisone or equivalent	≤ 20 mg per day (or ≤ 140 mg/week)	≥ 4 weeks
Corticosteroids	Topical for scalp only	Limit to 2 applications per day	≥ 3 weeks
Non-steroidal immunomodulatory (limited to one)	Intravenous immunoglobulin	2 g/kg per month	≥ 12 weeks
	Oral mycophenolate mofetil	3 g per day	≥ 12 weeks
	Oral cyclophosphamide	5 mg/kg per day	≥ 12 weeks
	Oral cyclosporine	3 mg/kg per day	≥ 12 weeks
	Oral leflunomide	20 mg per day	≥ 12 weeks
	Oral tacrolimus	4 mg per day	≥ 12 weeks
	Oral or intramuscular methotrexate	25 mg per week	≥ 12 weeks
	Oral azathioprine	3 mg/kg per day	≥ 12 weeks

Interventions or potential dosage adjustments may be considered if a patient experiences a concerning AE related to the medications in Table 4.

Upward adjustments in dose for reasons other than for change in body weight, or downward adjustments to prevent toxicities should be discussed with the CRO Medical Monitor. Patients who require interruption, dose modification, or re-initiation of the therapies in Table 4 may remain on blinded study drug therapy.

If a patient had been on more than one non-steroidal immunomodulatory medication, they must have stopped administration of the additional non-steroidal immunomodulatory medications for at least the washout periods listed in Table 5. Start and stop dates and dose/regimen for washout of these medications prior to Screening must be recorded on source documentation and eCRF.

Table 5. Washout Period for Prohibited Concomitant Medications

Prohibited Medication	Washout Period Prior to Screening ^a
Methotrexate	At least 4 weeks
Leflunomide, cyclophosphamide, intravenous immunoglobulin	At least 12 weeks
Any other non-steroidal immunosuppressive agent including azathioprine, cyclosporine, mycophenolate mofetil, tacrolimus,	At least 8 weeks

^a Medications are prohibited for at least the specified washout period immediately prior to screening

9.3 Prohibited Concomitant Medications

The use of the following concomitant medications is prohibited during the 24 weeks of study drug treatment due to the possibility that they might confound interpretation of study results.

- Rituximab
- Intravenous corticosteroids
- Intravenous immunosuppressive drugs
- Any other monoclonal antibody, biologic agent, or investigational agent
- Antimalarial agent(s)
- Topical corticosteroids (excluding scalp)
- Live viral or bacterial (including BCG) vaccination during the course of the study or within 3 months after the last dose of study medication

9.3.1 Washout Period for Prohibited Medications

Medications listed in Table 6 are prohibited within the indicated washout period immediately prior to Screening. Start and stop dates and dose/regimen for use of prohibited medications during the year prior to Screening (Visit 1) must be recorded on source documentation and eCRF.

Table 6. Washout Period for Prohibited Concomitant Medications

Prohibited Medication	Washout Period Prior to Screening^a
Rituximab	At least 24 weeks AND B-cell counts (local testing) that are confirmed to be within normal limits
Intravenous corticosteroids	At least 12 weeks
Intravenous immunosuppressives	At least 12 weeks
Any other monoclonal antibody, biologic agent, or investigational agent	At least 12 weeks or 5 half-lives (whichever is longer)
Antimalarial agent(s)	At least 36 weeks
Topical corticosteroids (excluding scalp)	At least 2 weeks

^a Medications are prohibited for at least the specified washout period immediately prior to screening

10 EXPLANATION OF STUDY PROCEDURES

10.1 Pretreatment, Treatment and Follow-up Periods

No study-related procedures should be performed prior to the signature of the informed consent document(s). After a patient has completed the necessary screening assessments and has been confirmed to be eligible by the Investigator, the Baseline Visit (Visit 2/Week 1, Day 1) for the patient can be scheduled.

10.1.1 Screening Visit (Visit 1) and Screening Period

Once written informed consent is obtained, patients will be screened for eligibility for entry into the study based on the inclusion and exclusion criteria detailed in Section 7. Screening includes, as indicated in the SOE in Section 3, a full medical/surgical history, including information relating to any prior or existing medical conditions/surgical procedures that may be relevant to the patient's experience in the study. Demographic data and DM-specific medical history information will also be recorded. Patients will also undergo a full physical examination, vital signs and a 12-lead ECG tracing will be obtained, and height and body weight will be measured. In addition, the full CDASIv2 will be performed and skin photographs will be taken. Blood and urine will be collected for standard safety laboratory assessments as well as pregnancy testing, hepatitis B and C screening, and other safety laboratory assessments (Section 8.3.2).

As part of the patient's medical history, documented evidence of cancer and TB screening are required. Study participants must have a diagnostic evaluation for cancer if the diagnosis of DM was within 2 years prior to the Screening Visit. The evaluation should include all age- and gender-appropriate screening tests and either a CT of the chest, abdomen, and pelvis OR, alternatively, a PET/CT of the chest, abdomen, and pelvis if this is standard practice in the particular center. If a diagnostic evaluation for cancer has not been performed in patients for whom it is required, a PET/CT (chest, abdomen, and pelvis) should be performed during the Screening Period. The diagnostic evaluation for cancer must be normal for a patient to meet this inclusion criterion. Study participants also must have no evidence of active or latent TB after a diagnostic evaluation with a CXR OR chest CT and 1 of the following: a) a PPD skin test, b) a QuantiFERON blood test, or c) T-SPOT.TB blood test. If the diagnostic TB evaluation has not been performed within 12 weeks prior to the Screening Visit, it may be performed during the Screening Period. For the patient to be eligible, the results of the diagnostic TB evaluation should include a negative chest image and 1 of the following: a) a PPD skin test with \leq 5-mm induration, b) a negative (not detected) QuantiFERON result, or c) a negative T-SPOT.TB test. If the QuantiFERON result is indeterminate, the test may be repeated once. If the repeat QuantiFERON test is indeterminate, then a PPD skin test may be used to confirm patient eligibility. The PPD skin test is not an acceptable method of TB testing in Sweden.

Once a patient has met all eligibility criteria the site representative should access the IXRS system and supply the necessary information to obtain a patient treatment assignment (see Section 8.4) in anticipation of administration of the first dose of study drug at the Baseline Visit 2/Week 1, Day 1.

10.1.2 Baseline Visit (Visit 2, Day 1)

Before initiating treatment, each study participant will report to the clinic to complete study related procedures as outlined in the SOE in Section 3. Study drug will not be administered until all baseline assessments have been completed and collection of the pre-dose sample for determination of IMO-8400 plasma concentrations and baseline laboratory samples have been obtained. Baseline assessments include physical examination, vital signs, the full CDASIv2, IMACS CSMs, SF-36, Timed Function Tests, 5-D Itch Scale, 12-lead ECG, and skin biopsy. In addition, skin photographs will be taken. Subsequently the patient will receive the first dose of study drug, and the patient will have a 2-hour post-dose blood sample for determination of IMO-8400 plasma concentration. The patient will remain at the clinic until released by the Investigator approximately 4 hours after the first dose administration.

10.1.3 Treatment Period (Visit 2/Week 1 through Visit 25/Week 24)

The Baseline Visit 2/Week 1 is also Day 1 of the Treatment Period; patients will receive the first dose of study drug that day as described in Section 10.1.2. During the treatment period, each patient will return to the clinical research facility for Visit 6/Week 5, Visit 10/Week 9, Visit 14/Week 13, Visit 18/Week 17, and Visit 22/Week 21. During these visits patients will complete the assessments indicated in the SOE in Section 3. All scheduled assessments should be performed prior to dosing, unless otherwise specified. All CDASI assessments performed after the first dose of study drug will be done using the mCDASIv2.

With the agreement of the patient and the Investigator, doses during weeks not requiring clinic visits may be administered outside of the clinic (e.g., at the patient's home or workplace) by a visiting nurse who has been trained in the protocol and approved by Idera (Section 8.2.4). The patient's vital signs, AEs (including assessment for ISRs), and concomitant medications will be recorded by the visiting nurse during administration of study drug.

On dosing days, the planned injection site will be assessed for the presence of any ISRs to confirm the injection site is appropriate for use. All visits during the treatment period of the study have a visit window of \pm 2 days. There must be at least 5 days between doses.

10.1.4 End-of-Treatment Visit (Visit 26) and Early Termination Visit

The patient will return to the clinical research facility at Week 25 \pm 2 days (Visit 26) for the EOT Visit. If the patient discontinues prematurely (i.e., before Week 25) the procedures that would normally be performed at the Week 25 EOT Visit should be performed as an ET Visit before the patient leaves the study. Any patient who withdraws or is withdrawn from the study prematurely will be asked to complete the ET assessments (which are the same as the EOT Visit 26 assessments) within 5 days of the notification of withdrawal; these patients will also be asked to complete the EOS assessments (Visit 27/Week 29) 4 weeks (\pm 4 days) after completing the ET assessments.

It is intended that with Investigator approval, patients who successfully complete the EOT (Visit 26/Week 25 assessments may initiate receiving open-label IMO-8400 treatment upon signature of the informed consent document(s) if a separate open-label extension study is initiated. *Signed informed consent for participation in any extension study must be obtained prior to assessments and extension study dosing at Visit 26/Week 25.* Patients who do not enroll

in an extension study, including patients who withdraw from this study prematurely, will complete safety follow-up assessments at the EOS Visit (Visit 27/Week 29), 4 weeks (\pm 4 days) after completing EOT assessments.

10.1.5 End-of-Study Visit (Visit 27/Week 29)

All patients who discontinue study drug prematurely or decline participation in an open-label IMO-8400 extension study must return for an EOS Visit at the investigational site 4 weeks (\pm 4 days) after the last dose of study drug for final study-related evaluations.

10.1.6 Unscheduled Visits

Unscheduled visits and assessments may be conducted at Investigator discretion in response to new clinical observations or as follow-up to AEs.

10.2 Description of Assessments

The following sections describe the assessments that are necessary during the study. Rational for the appropriateness of selected assessments are provided in Section 17.

10.2.1 Informed Consent

The Investigator must inform each prospective patient of the nature of the study, explain the potential risks, and obtain written informed consent from the patient prior to performing any study-related screening procedures.

10.2.2 Inclusion/Exclusion Criteria

All patients must meet all of the inclusion criteria specified in Section 7.1 and none of the exclusion criteria specified in Section 7.2 to be enrolled in this study. As noted in Section 7.3, under some circumstances, patients who fail to meet eligibility criteria during the Screening Period may be rescreened for study entry following discussion with the CRO's Medical Monitor.

10.2.3 Demographic Information and Medical History

Basic demographic information (e.g., date of birth, age, sex, race) will be collected and a detailed medical history, including review of past and ongoing medications and therapies, history of alcohol use, and smoking history will be obtained at the Screening Visit as specified in the SOE in Section 3.

The Investigator should review the study candidate's medical history, including details relating to DM and any other medical conditions. As part of the patient's medical history, documented evidence of cancer and TB screening are required. Information regarding current medications must be captured on the eCRF. Details regarding any medication received within 3 months prior to screening will be collected on the eCRF. Information on permitted and prohibited medications, doses, and regimens are provided in Section 9.

10.2.4 Physical Examination Including Weight and Height

Physical examinations will be conducted at the time points specified in the SOE provided in Section 3. Physical examinations will be performed by the Investigator, an MD Sub-Investigator, a Nurse Practitioner, or a Physician's assistant (if licensed in the state to perform physical

examinations); if possible, the same person should perform all examinations for a given patient. Physical examinations will include examination of general appearance, head, eyes, ears, nose, and throat (HEENT), heart, lungs, chest, abdomen, skin, lymph nodes, musculoskeletal, and neurological systems.

Height is measured in centimeters, without shoes, at the Screening Visit only. Weight should be recorded in kg and will be measured during all physical examinations.

10.2.5 Skin Photography

Photography of the areas of the skin assessed in the CDASIV2 will be taken at Screening (Visit 1), Baseline (Visit 2/Week 1, prior to initiation of study drug treatment), and at the EOT/ET Visit 26/Week 25 as described in the SRM. Permission to perform photography will be requested in the informed consent document(s). Subjects who refuse being photographed may still participate in the study.

The SRM and additional documents will provide instructions on skin photography procedures.

10.2.6 Cutaneous Dermatomyositis Disease Area and Severity Index (CDASI)

The full CDASI version 2 (CDASIV2) assessment will be performed at the Screening and Baseline Visits. Subsequent CDASI assessments will be performed using the mCDASIV2, which eliminates the abdominal skin assessments post-injection. The mCDASIV2 will be performed by trained raters blinded to treatment assignment at the time points specified in the SOE in Section 3. To further decrease the risk of unblinding, patients will be provided with an abdominal covering to mask injection sites when the mCDASIV2 is performed

The CDASIV2 is a clinician administered, one-page instrument designed to evaluate the cutaneous manifestations of DM (see Appendix 4). Developed by leading academic dermatologists and rheumatologists with an expertise in DM, it takes approximately 5 minutes to complete and its validity and reliability have been demonstrated in multiple studies of DM patients (Klein 2008, Yassaee 2010, Goreshi 2012).

The CDASI includes separate measurements for disease activity and damage and yields a Total Score that captures overall disease state, an Activity Score that reflects the current inflammatory state of disease, and a Damage Score. Decreases in CDASI scores are indicative of improvement.

10.2.7 Skin Biopsy

Skin biopsies will be performed at the Baseline Visit 2/Week 1, Day 1, and at the EOT Visit 26/Week 25. Two 4 mm punch biopsies will be taken side by side on the upper back or upper arm of patients (whichever the Investigator feels has the most active skin disease at baseline) at baseline and in an adjacent area at the EOT biopsy. Sites where the baseline biopsy samples were taken should be photographed **PRIOR** to the baseline biopsy (no photographs will be taken after the biopsy) to document the disease activity and to guide the EOT biopsy site. Biopsies can be performed with or without local anesthesia, as considered appropriate for a specific patient or study site. The skin samples should be prepared for analyses as per the procedures described in the Laboratory Manual. The skin biopsy is not required for a premature discontinuation visit.

10.2.8 International Myositis Assessment Clinical Study (IMACS) Core Set Measures

The IMACS Group, which includes more than 100 adult and pediatric rheumatologists, neurologists, dermatologists, rehabilitation medicine physicians, statisticians, nurses, and others with expertise in myositis, was founded in 2000 to facilitate clinical research for the idiopathic inflammatory myopathies including DM. The IMACS Group has identified a core set of outcome measures (the CSMs) to comprehensively describe myositis disease activity in juveniles and adults. The IMACS Group has also identified preliminary DOIs in disease activity (Rider 2004), which reflect clinically meaningful change in each of the CSMs. The subset of the CSMs identified by IMACS that will be used in this study are briefly described in Sections 10.2.8.1 and Section 10.2.8.2.

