6.1.2 Exploratory Endpoints

6.1.2.1 Exploratory Efficacy Endpoints

- Change from baseline in the following International Myositis Assessment Clinical Study (IMACS) “Core Set Measures” (CSMs). Improvement will be assessed using the IMACS group definitions of improvement (DOIs) (2004 DOI [Rider 2004]):
 - Manual muscle testing-8 (MMT8)
 - Serum creatine kinase (CK), aldolase (ALD), lactate dehydrogenase (LDH), alanine transaminase (ALT) and aspartate transaminase (AST)
- Change from baseline in the following Timed Function Tests:
 - 10-meter walk-run test (10MWR)
 - Timed up and go test (TUG)
 - 4 stair climb test
- Change from baseline in the Short Form-36 Health Survey (SF-36)
- Change from baseline in the 5-D Itch Scale

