14.4.4 Efficacy Analyses

The primary efficacy endpoint will be assessed via an RMMM. An appropriate covariance structure for repeated measures will be used. The difference between each IMO-8400 treatment group and placebo at Week 25 will be assessed. The overall alpha level will be controlled using the Bonferroni-Holm step-down method. Further details of this analysis will be described in the SAP. A sensitivity analysis will be performed to test the effect of important covariates on the effect of IMO-8400 using an RMMM.

Differences in response rate between the IMO-8400 treatment groups and placebo will be assessed via logistic regression.

The MMT8, TUG, 4 stair climb test, timed 10MWR test, serum CK, ALD, LDH, AST, ALT, SF-36, and 5-D Itch Scale will be analyzed in a similar manner to the primary endpoint.

For the proportion of patients who meet the IMACS 2004 DOI (Rider 2004) at EOT, logistic regression will be performed.

All efficacy endpoints will also be summarized descriptively by treatment group and nominal visit. Other exploratory and sensitivity analyses will be specified in the SAP in addition to further details regarding the statistical methodology.

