17.3.2.1 Manual Muscle Testing (MMT8)

Manual muscle testing is used to evaluate the function and strength of individual muscles and muscle groups based on the effective performance of a movement against gravity or manual resistance and is 1 of the IMACS CSMs for DM. The MMT has been widely used in myositis therapeutic trials and clinical studies (Feldman 2008, Jain 2006, Amato 2011) and its reliability and validity have been demonstrated repeatedly (Cuthbert 2007, Rider 2011). Moreover, the IMACS group identified muscle strength assessment as a key measure for clinical trials (Miller 2001).

The MMT8 is less physically and mentally taxing for the patient and clinician, has excellent internal and inter-rater reliability, and performs as well as or better than Total MMT in terms of responsiveness, content validity, and construct validity, it is expected to be an even more reliable indicator of muscle strength than the full MMT and has been incorporated into the IMACS CSM (<https://www.niehs.nih.gov/research/resources/imacs/diseaseactivity/>). While an absolute value for the minimal clinically important difference has not been determined for the MMT or MMT8, a group of adult and pediatric rheumatologists and neurologists have reached consensus that MMT should improve by $\geq 15\%$ to classify an adult DM/PM patient as improved and should improve by $\geq 18\%$ to classify a juvenile DM/PM patient as improved (Rider 2004).

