17.3.2.2 Muscle Enzyme Levels

Muscle enzyme levels are another of the IMACS CSMs. Per IMACS, increases from Baseline in at least 2 of the following muscle enzymes is associated with a clinical improvement in DM: CK, LDH, AST, ALT, or ALD. Improvement is defined as changes from Baseline in LDH of $\geq 25\%$, and changes from Baseline in CK, AST, ALT, and ALD of $\geq 30\%$ (Rider 2004).

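### The single proportion meeting the IMACS 2004 definition of improvement is named after a definition wider than the two core set measures collected; report improvement by component instead

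*Protocol*

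**What the plan says.** - **The definition.** Protocol 10.2.8 describes a "core set of outcome measures (the CSMs) to comprehensively describe myositis disease activity in juveniles and adults". It adds that IMACS has definitions of improvement (DOIs), "which reflect clinically meaningful change in each of the CSMs".
- **What is collected.** The same paragraph goes on to "The subset of the CSMs identified by IMACS that will be used in this study", and subsections 10.2.8.1 and 10.2.8.2 name MMT8 and muscle enzymes. Section 6.1.2.1 lists the same two under the core set measures. SF-36, the timed function tests and the 5-D Itch Scale are listed there as separate endpoints.
- **What is analysed.** Section 14.4.4 specifies logistic regression at end of treatment: "For the proportion of patients who meet the IMACS 2004 DOI". The synopsis says the same.
- **The rules supplied.** Section 17.3.2.1 gives an MMT improvement of at least 15% "to classify an adult DM/PM patient as improved". Section 17.3.2.2 requires change "in at least 2 of the following muscle enzymes", with thresholds of 25% for LDH and 30% for CK, AST, ALT and ALD. Each rule is stated for its own measure.

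**The concern.** The analysis section takes the name of a definition that, in the protocol's own description, spans the whole core set, while the schedule orders only part of that set. A response rate reported as the IMACS 2004 DOI would be taken for the published criterion and could be set beside rates from other myositis studies. In fact it would rest on MMT8 and enzymes alone. An SAP can settle how variables are derived, but it cannot supply measures that the protocol does not collect.

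The rate under that name would also depend on how the two components are combined, so the label does not identify one quantity.

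**Working it through.** The plan states no figure for this endpoint, and the sample size rests on the CDASI alone, so there is nothing to reproduce. The check is mainly a comparison of sections.

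**1. Scope against data.** Section 10.2.8 has the DOIs covering each core set measure and the study using a subset. Sections 6.1.2.1, 10.2.8.1 and 10.2.8.2 and the Schedule of Events agree that the subset is MMT8 and enzymes. Section 14.4.4 nevertheless refers to patients who meet the DOI, in the singular and without qualification.

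**2. Two readings of the DOI.**
- *One patient-level rule over the core set.* The result would then be a rule on part of the set, carrying the name of the whole.
- *One definition per measure.* Sections 6.1.2.1 and 10.2.8 use the plural, and 17.3.2.1 and 17.3.2.2 give a criterion for each measure. All the inputs are collected, but they yield two proportions, not one.

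On either reading, the outcomes that the data and the stated rules support directly are the two component improvements.

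**3. How far a single rate can move (illustration).** The protocol gives no component response rates. Assume each component is met by 30% of patients, with 12 patients per group (14.2).
- Independent components: either = 1 − 0.7² = 0.51, or 12 × 0.51 = 6.1 patients. Both = 0.3² = 0.09, or 12 × 0.09 = 1.1 patients. The gap is 42 percentage points.
- Complete overlap: either = both = 0.30, so the gap is 0.
- No overlap: either = 0.30 + 0.30 = 0.60 and both = 0, so the gap is 60 points.

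Under independence, with assumed rates of 10% to 30% for MMT8 and 10% to 40% for enzymes:

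| Rule | Lowest | Highest |
|---|---|---|
| Both | 0.1 × 0.1 = 1% | 0.3 × 0.4 = 12% |
| Either | 0.1 + 0.1 − 0.01 = 19% | 0.3 + 0.4 − 0.12 = 58% |

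These figures describe the joining rule only. They do not measure the effect of the core set measures left out, which the documents give no means of estimating.

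**4. Why the components behave differently here.** Muscle weakness is not required for entry (7.1, criterion 5), and MMT8 has a maximum of 80 (Appendix 5). Section 17.3.2.1 does not say what the 15% is a percentage of.
- Relative to baseline, no patient starting above 80 / 1.15 = 69.6 can reach it.
- As a share of the scale, 0.15 × 80 = 12, so no patient starting above 80 − 12 = 68 can reach it.

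Requiring both components makes such patients automatic non-responders. Requiring either leaves them judged on enzymes alone.

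**5. Direction of enzyme change.** Section 17.3.2.2 associates a rise from baseline in at least two enzymes with clinical improvement, and its next sentence gives thresholds for change without a direction. Inclusion criterion 5a uses elevated CK or ALD as evidence of active muscle involvement. Appendix 3 lists elevated muscle enzymes among the diagnostic criteria. These cannot all guide the same variable as written.

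**The case against.** The strongest reply is that the per-measure reading is the natural one. The protocol speaks of DOIs in the plural, attaches them to the two listed measures and gives a criterion for each. Every input is then collected, and only the singular wording in 14.4.4 and the synopsis is loose. The use of a subset is disclosed, no comparison with published rates is planned, and the endpoint is exploratory. How components are joined is ordinary SAP content, and 14.4.4 defers methodological detail to the SAP.

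Most of this stands. A missing joining rule would not by itself be a finding, and the illustration in the working carries no more weight than that. The exploratory status limits the consequences. But the per-measure reading supports reporting two proportions, not one result under the definition's name, and disclosing the subset in 10.2.8 does not correct the label in 14.4.4.

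A reader might go further and infer that the DOI cannot be evaluated at all from MMT8 and enzymes, so that the endpoint is undeliverable. The documents do not support that. The protocol neither lists the full core set nor says how many measures the DOI requires, and the source that would settle it is not at hand.

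**Conclusion.** The point holds as a mislabelled exploratory responder endpoint. The protocol's own text has the DOIs covering each core set measure, has the study using two of those measures, and gives a separate rule for each. That supports improvement by component, but not a single response called the IMACS 2004 DOI.

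Severity is minor: the primary endpoint, its multiplicity control and the sample size are untouched. No effect size can be taken from the documents. The gap of 0 to 60 percentage points between the two joining rules (42 under independence) rests on an assumed 30% rate for each component. The inconsistency over the direction of enzyme change does not depend on any assumption and affects any enzyme-based outcome.

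**What to change.** In 6.1.2.1, 14.4.4 and the synopsis, replace the single proportion with two separately analysed exploratory outcomes: the MMT8 improvement threshold and the muscle-enzyme improvement threshold. Label both as component thresholds. If a composite is kept, call it study-specific, state its joining rule in the SAP, and do not present it as the IMACS 2004 DOI or compare it with published DOI rates.

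Reconcile the direction of enzyme change in 17.3.2.2 with inclusion criterion 5a and Appendix 3 before the enzyme component is computed.

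The cost is a wording change, one more table and the loss of a recognised label for an exploratory endpoint. Assessments, visits and sample size do not change.
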